The primary aim is: To evaluate the safety and tolerability of fecal transplant through rectal and oral capsular routes in cirrhosis and HE from a liver disease and symptom standpoint using analysis of serious adverse events, especially HE recurrence, in a placebo-controlled trial.

Secondary aims are between the groups:

- 1. Safety and tolerability of FMT compared to placebo
 - a. Frequency, severity and relatedness of solicited and unsolicited AEs through day 30
 - b. Occurrence of new potentially transmitted infections through six-months post FMT
 - c. Occurrence of new onset or significant worsening of chronic medical conditions post-FMT
- 2. To define the changes in microbiota composition and function of the stool microbiota after FMT compared to pre-FMT baseline and donor compared to placebo

- 3. To evaluate changes in systemic inflammatory cytokines and endotoxin, quality of life and cognitive function compared to pre-FMT baseline and compared to placebo
- 4. To determine occurrence of new onset or significant worsening of chronic medical conditions through six months post-FMT and compared to placebo
- 5. To evaluate the changes in the microbiota after the second oral FMT vs. placebo compared to baseline values

Inclusion/Exclusion Criteria:

Inclusion criteria:

- A. Cirrhosis diagnosed by either of the following in a patient with chronic liver disease
 - a. Liver Biopsy
 - b. Radiologic evidence of varices, cirrhosis or portal hypertension
 - c. Laboratory evidence of platelet count <100,000 or AST/ALT ratio>1
 - d. Endoscopic evidence of varices or portal gastropathy
 - e. Fibroscan values suggestive of cirrhosis
- B. On treatment for hepatic encephalopathy (patient can be on lactulose and rifaximin)
- C. Age: at least 21 years of age
- D. Able to give written, informed consent (demonstrated by mini-mental status exam>25 at the time of consenting)
- E. Women of child bearing potential must agree to use effective contraception for the duration of the study and for 10 days prior and 30 days after the study
- F. Negative pregnancy test in women of childbearing age

Exclusion criteria:

- A. MELD score >22
- B. WBC count <1000 cells/mm3
- C. Platelet count < 25,000/mm3
- D. TIPS in place for less than a month
- E. Currently on antibiotics apart from rifaximin
- F. Infection at the time of the FMT (diagnosed by blood culture positivity, urinalysis, paracentesis as needed)

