- G. Hospitalization for any non-elective cause within the last 1 month
- H. Patients who are aged >75 years
- I. Patients who are pregnant or nursing (will be checked using a urine pregnancy test)
- J. Patients who are incarcerated
- K. Patients who are incapable of giving their own informed consent

- L. Patients who are immuno-compromised due to the following reasons:
 - a. HIV infection (any CD4 count)
 - b. Inherited/primary immune disorders
 - c. Current or recent (<3 mos) treatment with anti-neoplastic agent
 - d. Current or recent (<3 mos) treatment with any immunosuppressant medications [including but not limited to monoclonal antibodies to B and T cells, anti-TNF agents, glucocorticoids, antimetabolites (azathioprine, 6-mercaptopurine), calcineurin inhibitors (tacrolimus, cyclosporine), mycophenolate mofetil]. Subjects who are otherwise immunocompetent and have discontinued any immunosuppressant medications 3 or more months prior to enrollment may be eligible to enroll.
- M. Patients on renal replacement therapy
- N. Patients with untreated, in-situ colorectal cancer
- O. Patients with a history of chronic intrinsic GI diseases such as inflammatory bowel disease (ulcerative colitis, Crohn's disease or microscopic colitis), eosinophilic gastroenteritis or celiac disease
- P. Major gastro-intestinal or intra-abdominal surgery in the last three months
- Q. Patients who have received FMT within last 6 months

Other Exclusion Criteria:

Enema-related

- (1) Platelet count<25,000
- (2) Grade IV hemorrhoids

Safety-related:

- (1) Dysphagia
- (2) History of aspiration, gastroparesis, intestinal obstruction
- (3) Ongoing antibiotic use (except for Rifaximin)
- (4) Severe anaphylactic food allergy
- (5) Allergy to ingredients Generally Recognized As Safe in the FMT capsules (glycerol, sodium chloride, hypromellose, gellan gum, titanium dioxide, theobroma oil)
- (6) Adverse event attributable to prior FMT
- (7) ASA Class IV or V
- (8) Pregnant or nursing patients
- (9) Acute illness or fever within 48 hours of the day of planned FMT
- (10) Immunocompromised due to medical conditions
- (11) Probiotics use within the last 48 hours of the day of planned FMT
- (12) Any condition that the physician investigators deem unsafe, including other conditions or medications that the investigator determines puts the participant at greater risk from FMT

Intervention

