Visit 4: All procedures as in visit 2 will be performed again, including dietary recall, targeted physical exam, and sample collection. All subjects will also get another oral FMT/placebo dose of 5 capsules each depending on their original assignment. All subjects in the study will get this intervention unless (a) they refuse the intervention (b) have undergone a liver transplant or have died/discharged to hospice (c) developed an infection or an SAE that was adjudicated to be related to FMT in the interim or (d) are currently undergoing antibiotic therapy for an infection that is not related to FMT.

For those who are infected due to an FMT-unrelated infection, we will approach the patients 2 days after the completion of the assigned antibiotic course. For those initiated on SBP (Spontaneous Bacterial Peritonitis) prophylaxis, we will provide the intervention after the initial SBP episode is treated. This may require delaying the intervention from day 30 to up to day 45 but this will still be counted as the second FMT.

All other subjects will be given the intervention and the blind will still be maintained. The brain function tests and QOL will be performed again. Groups 1 and 2 will get active FMT and groups 3 and 4 will get placebo FMT. No enemas will be given. The subjects will then be sent home.

Follow-up visits every month: The subjects will be followed monthly in person, or by phone or videoconference at Months 3, 4, 5 to evaluate dietary and medication changes and for safety analysis (hospitalizations, AEs or SAEs), targeted physical exam and for collection of samples at each study clinic visit. Mail-in kits for collection of stool, and urine will be provided along with instructions for use if visit is performed remotely. We will also perform the cognitive tests and QOL assessment at one month post-second intervention and at 6 months. We will continue to follow every patient for 6 months regardless of whether they developed an SAE or hospitalization in between. Only reasons not to follow them up for 6 months would be death, liver transplantation or patient withdrawal of consent.

End-of-Study visit: Per FDA mandates for FMT studies, we will see the patients at six months and we will evaluate AEs, interim hospitalizations, dietary recall, and perform targeted physical exam, QOL and brain function studies, and collect serum, and stool again. At this point the participation of the patient will end.

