Specific safety findings will result in temporarily suspending enrollment until a safety review is convened, the objective of which is to determine whether the study should continue per protocol, proceed with caution, be further investigated, be discontinued, or be modified and then proceed. Suspension of enrollment is another potential outcome of a safety review. This will be done if the assigned infection is in the FMT group since this patient population is prone to infections.

Subsequent review of serious, unexpected, and related AEs by the Data and Safety Monitoring Board, IRB, the PI, or the FDA or relevant local regulatory authorities may also result in suspension of further trial interventions/administration of FMT at a site. The FDA and PI retain the authority to suspend additional enrollment and study interventions/administration of FMT for the entire study, as applicable. The PI and the adjudication panel will make the initial decision. The subsequent safety review by the IRB and FDA will then decide if the study can resume.

Findings that will trigger a safety review are

Findings that will trigger a safety review are

- o Death related to FMT material or study procedures in any subject;
- New potentially transmitted infection in five or more subjects assigned to FMT - i.e., cannot exdude transmission and/or attribution is

pending investigation/Data Monitoring Committee (DMC) adjudication;

- Any single potential transmitted infection assessed as possibly, probably, or definitely related to FMT by the investigator and DMC.
- One or more subjects assigned to FMT has a serious, unexpected AE assessed as possibly, probably, or definitely related to FMT by the investigator and DMC; Five or more subjects (per assigned group) develop a new diagnosis of a medical condition or immune-mediated disease considered probably, or definitely related to FMT.
- Five or more severe AEs of a similar nature occurring in different subjects and assessed as definite, possible or probable relatedness to study product in groups assigned to FMT (per assigned group)

FDA/CBER will be notified by phone or fax within 72 hours if the study is halted for review.

Individual study halting rules

- (1) patient's choice
- (2) change in GI adverse events with a magnitude of 3 increase over baseline
- (3) fever and signs of infection (including WBC count >12,000/ml)
- (4) SAE development including cirrhosis complications (OHE) and hospitalizations for

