Suspected adverse reaction means any adverse event for which there is a reasonable possibility that FMT caused the adverse event. For the purposes of IND safety reporting, 'reasonable possibility' means there is evidence to suggest a causal relationship between FMT and the adverse event. A suspected adverse reaction implies a lesser degree of certainty about causality than adverse reaction, which means any adverse event caused by a therapy.

6. Unexpected

An adverse event or suspected adverse reaction is considered "unexpected" if it is not listed in the Investigator brochure or is not listed at the specificity or severity that has been observed; or is not consistent with the risk information described in the general investigational plan or elsewhere in the current application.

Solicited Adverse Events

According to the attached Adverse Event Grading Chart

Monitoring of Adverse Events

Each subject will be monitored for the occurrence of AEs, including SAEs. Each subject will be followed for safety monitoring at each follow-up interval and at the 6-month phone call

- Subjects will be questioned regarding stool patterns, abdominal pain, fevers, and subjective well-being. Subjects will be questioned about the possible occurrence of adverse events in a generalized way, such as, "How have you been feeling since your last visit?" Subsequent solicited questions and relevant details will be asked if there is a positive response. Site Investigators will be contacted by study representative if there is a suspected or reported AE
- Subjects having AEs will be monitored with relevant clinical assessments and laboratory tests, as determined by the site Investigator
- AEs, actions taken as a result of AEs, and follow-up results will be recorded as well as in the subject's source documentation. Follow-up laboratory results should be filed with the subject's source documentation
- Subjects will be seen every month till 6 months post-enrollment to record any SAEs, new onset of potentially transmitted infections, new medical conditions, or changes in pre-existing medical conditions (New onset or significant worsening of chronic medical conditions including, but not limited to, autoimmune diseases, inflammatory bowel diseases, metabolic syndrome, cardiovascular disorders, and neuropsychiatric disorders.)

Assessment of Adverse Events

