The Investigator is to report any safety observations from the list above to the Sponsor within **7 days** of becoming aware of the event. The Sponsor will notify the FDA in its *Annual Report*. Any observation that is also an AE will be recorded on the subject's case report form along with any actions taken. If not all information is available at the time of initial report, follow up SAE reports will be completed and submitted. The investigator will report all new onset of potentially transmitted infections and new onset or significant worsening of chronic medical conditions to FDA regardless of the assessment of causality and according to time frames outlined in 21 CFR 312.32 (within 7 days for deaths and life-threatening SAEs; others within 15 days). Similarly, deaths and SAEs related to FMT procedures (not only FMT material) will be reported to the FDA expeditiously (within 7 days for deaths and life-threatening SAEs; others within 15 days.

The Investigator/Sponsor is to report any safety observations from the list above to the local IRB within **5 days** of becoming aware of the event. The Investigator/Sponsor will notify the FDA in its *Annual Report*. Any observation that is also an AE will be recorded on the subject's case report form along with

any actions taken. If not all information is available at the time of initial report, follow up SAE reports will be completed and submitted.

The Investigator/Sponsor is required to follow SAEs until resolution, regardless of whether the subjects are still participating in the study. Resolution is defined as:

- Resolved with or without residual effects
- Return to baseline for a pre-existing condition
- Fatal outcome; if autopsy is performed, the autopsy report must be provided to the Investigator/Sponsor.

Monitoring the study database and submitting safety reports

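### Follow-up may end at liver transplantation, which conflicts with the plan's own commitment to collect infections and SAEs from all subjects for six months

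*Combined protocol and SAP*

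**What the plan says.** The paragraph on monthly follow-up visits commits the trial to six months for every patient, whatever SAE or hospitalization occurs, and then sets the exceptions: "Only reasons not to follow them up for 6 months would be death, liver transplantation or patient withdrawal of consent". The protocol expects some transplants early on, because Visit 4 lists patients who "have undergone a liver transplant or have died/discharged to hospice" among those who do not receive the second intervention.

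Other sections make commitments without a transplant exception:

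- Secondary aim 1b: "Occurrence of new potentially transmitted infections through six-months post FMT".
- Monitoring of Adverse Events: "Subjects will be seen every month till 6 months post-enrollment to record any SAEs, new onset of potentially transmitted infections".
- The Procedures overview, just before Figure 1, promises monthly visits to six months for all subjects, to assess SAEs.
- Reporting of safety observations: "The investigator will report all new onset of potentially transmitted infections and new onset or significant worsening of chronic medical conditions to FDA", whatever the causality assessment.

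The list of findings that trigger a safety review includes "Any single potential transmitted infection assessed as possibly, probably, or definitely related to FMT by the investigator and DMC".

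Exclusion criterion L.d bars "Current or recent (<3 mos) treatment with any immunosuppressant medications", and its examples include "calcineurin inhibitors (tacrolimus, cyclosporine), mycophenolate mofetil".

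**The concern.** Death makes further follow-up impossible, and withdrawal of consent makes it unauthorised. Transplantation does neither, yet the three are treated alike. Patients who have an SAE, are hospitalized or are withdrawn before day 30 all stay in safety follow-up. A transplanted patient need not.

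The safety data at stake are infections and SAEs between transplant and month 6. The protocol treats immunosuppressant treatment as a reason not to give FMT. The documents do not say that transplant recipients receive such drugs, but that is ordinary practice. A subject transplanted after dosing would then enter a state for which the protocol would have refused enrolment, and could leave observation at that point.

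There is also an analysis question. The primary endpoint covers FMT-related SAEs including HE recurrence within six months, and HE episodes are compared by chi-square or Fisher tests. The plan does not say how a patient transplanted before any HE recurrence is counted.

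**Working it through.** The plan gives no figure on this point to reproduce: no transplant rate and no post-transplant infection rate. The check is mainly a comparison of sections, followed by an illustration of size.

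**Does another section restore what the follow-up rule removes?**

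1. Individual study halting rules: a subject withdrawn before day 30 is still followed to month 6 for safety, and non-elective hospitalization is one of the halting criteria. An unplanned transplant admission before day 30 could fall under this. A later transplant, or one classed as elective, does not.
2. SAE follow-up to resolution, under the reporting rules: this applies even when the subject is no longer in the study, so it covers events already open at transplant. If the transplant admission is itself an SAE, it covers that episode. It does not provide a search for new infections afterwards.
3. FDA reporting of new potentially transmitted infections: the duty is not limited to subjects still attending, but without contact the investigator has no planned way to learn of an infection.
4. Aim 1b, the Procedures overview and Monitoring of Adverse Events promise six months without exception. The follow-up paragraph makes an explicit exception. They cannot all stand as written.

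**How many patients?**

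Inputs: 25 per group (Sample size) and three groups with at least one active FMT route, so 3 × 25 = 75 recipients. Assumptions: 2% to 8% transplanted within six months, with times spread evenly, so that each loses 3 months on average.

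- Planned person-months: 75 × 6 = 450.
- Recipients leaving early: 75 × 0.02 = 1.5, and 75 × 0.08 = 6.
- Person-months lost: 1.5 × 3 = 4.5, or 4.5/450 = 1.0%; 6 × 3 = 18, or 18/450 = 4.0%.
- Even at 10%: 7.5 × 3 = 22.5, or 22.5/450 = 5.0%.
- All four arms at 2% to 8%: 2 to 8 of 100, since the rule applies to placebo patients too.

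**How far could the counting rule move a proportion?**

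In an arm of 25, one patient is 1/25 = 4 percentage points. This is a ceiling. It applies only if the patient would otherwise have had an event; if not, the shift is zero. The documents give no HE-recurrence rate, so the assumed hospitalization rates serve only to show the effect of dropping one event-free patient from the denominator:

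- 80%: 20/25 = 80.0% against 20/24 = 83.3%, a difference of 3.3 points.
- 30%: 7.5/25 = 30.0% against 7.5/24 = 31.25%, a difference of 1.25 points.
- 10%: 2.5/25 = 10.0% against 2.5/24 = 10.4%, a difference of 0.4 points.

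**The case against.** The strongest objection is that this is a small matter of wording. Several sections already promise follow-up to six months, open SAEs are followed off study, and few transplants are likely. MELD above 22 and recent non-elective hospitalization are exclusions, the background says HE no longer gives transplant priority, and all 20 subjects in the prior enema trial completed five months. Post-transplant infections also have other causes. The causality rules call an event related only if FMT explains it better than another cause does, so such infections may say little about FMT.

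Much of this stands. The numbers are probably small, although 20 completers do not settle the rate: at 8%, the chance of no transplant among 20 is 0.92^20 = 0.19. Difficulty of attribution is a reason to tabulate these infections separately. It is not a reason to leave them uncollected, because FDA reporting does not depend on causality. The other sections supply only partial cover, and the explicit exception remains.

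A reader might infer three stronger claims that the documents do not support:

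- **That the plan counts transplanted patients as event-free.** No section says so. Exclusion, separate counting and counting as an event are all compatible with the text. For hospitalization, an unplanned transplant admission might itself be an event under the safety and hospitalization analysis.
- **That patients leave when their risk is highest.** The documents give no post-transplant risk, and exclusion L.d governs who may receive FMT, not later risk.
- **That surveillance is lost altogether, or that the main safety conclusion is undermined.** The partial cover and the few percent of person-months do not show this.

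**Conclusion.** The concern holds as a conflict between sections, in which a stated rule gives up obtainable safety data. The follow-up paragraph allows follow-up to end at transplantation, against aim 1b, the unqualified monthly follow-up and the infection-reporting duty. The existing provisions cover only subjects withdrawn before day 30 and SAEs already open.

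The quantity of data lost is probably small: 1.5 to 6 of 75 recipients and about 1% to 4% of person-months, resting on the assumed 2% to 8% rate and evenly spread transplant times. It still matters because one review trigger has a threshold of a single infection judged at least possibly related. The chance of missing such a case cannot be calculated from the documents.

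On analysis, the supportable conclusion is that the handling of transplant is unspecified. Its effect on an arm's HE-recurrence proportion is at most 4 points per patient and may be zero. The change is worth making because it is cheap.

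**What to change.** 1. Remove liver transplantation from the reasons to end safety follow-up, and reconcile that paragraph with aim 1b, the Procedures overview, Monitoring of Adverse Events and the reporting rules.
2. After transplant, continue monthly phone or record contact for deaths, SAEs and infections to month 6. Remote contact is already allowed at months 3 to 5, and Monitoring of Adverse Events already mentions a six-month phone call.
3. Tabulate post-transplant events separately by arm, and list transplants by arm.
4. State before unblinding how transplant is counted in the six-month HE-recurrence comparison, for example as a competing or separately counted outcome.

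The cost is a short protocol amendment, a sentence in the analysis section, and a few calls or chart reviews per transplanted patient. The drawback is that post-transplant infections have other causes and will be hard to attribute; separate tabulation keeps them from being mixed with the rest. These changes concern data collection and analysis only.
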